Are investigational drugs, devices, or biologics (test articles) controlled by the Principal Investigator? (See FDA IND and IDE Guidance for information regarding test article control).	 Yes  No If "Yes", describe your plan for control of the test article:	
List any approved drugs, biologics and/or devices being studied:		
G. Other Approvals/Regulated Materials: Does this research involve the use of the regulated materials listed below? If "Yes", additional approvals may be required.		 Yes  No

 - Controlled Substances - Radiation - Human Embryonic Stem Cells – The WHHS IRB cannot approve stem cell research - Fetal Tissue – The WHHS IRB cannot approve research involving fetal tissue 		

PART 2: STUDY DESIGN

Complete items A-E using clear, concise, non-technical, lay language (i.e., the type of language used in a newspaper article for the general public) wherever possible. Define all acronyms.

Space limits are recommendations and should be adjusted as needed, but the total length for sections A-E should not exceed 5 pages.

A. Synopsis (Briefly summarize the research.)	Space limit: quarter page
--	---------------------------

Study Description: This is a randomized prospective study comparing two postoperative leg sleeves. The novel bioactive sleeve (Reparel Leg Sleeve) will be compared to a regular TED stocking. The main hypothesis for this study is that postoperative use of a novel bioactive sleeve after hip replacement will decrease pain and improve patient reported outcome scores faster and more reliably than the control standard TED stocking. In order to test this hypothesis, approximately 50 patients scheduled for hip replacement will be randomized to one of two arms (bioactive sleeve on operative leg and TED stocking on other, versus bioactive sleeve on nonoperative leg and TED stocking on operative leg). The following standard assessment tools will be assessed: patient reported outcomes (VAS, HOOS JR, VR12, and HSS, Satisfaction, Forgotten Joint), study questionnaire. PROMs will fall under chart review activities.

Objectives:

Primary Objective: Assessing the effectiveness of a bioactive sleeve against a non-bioactive TED leg sleeve with regard to pain, swelling, and dvt rates.

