Primary Endpoint: Patient reported outcome scores (VAS, HOOS JR, VR12, HSS, Satisfaction, Forgotten Joint).

Secondary Endpoints: Swelling evaluated by routine clinical evaluations. DVT rates monitored.

Study Population: This prospective study hopes to enroll approximately 50 male and female patients over the age of 18 years old and below the age of 90 years old. BMI must be below 40. Subjects volunteer for participation with elective hip replacement.

Description of Study Intervention: This is a device study using a novel bioactive sleeve which is assumed to mimic the effects of photobiomodulation in comparison to a placebo sleeve.

Study Duration: Study duration from when the study opens until the completion of data analysis is expected to be 24 months.

B. Purpose (Specify the hypotheses and/or objectives.)	Space limit: half page
---	------------------------

This prospective study will evaluate pain, swelling, dvt rates as well as narcotic use in post-operative total hip arthroplasty patients using novel non-compressive photobiomodulating stocking (NCPS) versus current standard of care gradient compression stocking (Thrombo-Emolic-Deterrent or TED hose). Disadvantages of standard TED stockings are difficulty of placement, and thereby compliance in the postoperative period. Current literature remains mixed regarding the effectiveness of these stockings in pain, swelling, and dvt reduction. This study will evaluate if NCPS is equivalent, or superior, in these outcome areas, and it may provide a new and comfortable way to reduce patient pain and swelling immediately following hip surgery.

C. Background (Summarize previous research. Explain the rationale for the proposed investigation and if applicable how this research differs from local standard of care.)

Space limit: one page

Total hip arthroplasty (THA) is one of the most common surgical procedures today. It is designed and proven to effectively reduce pain caused by end-stage osteoarthritis. Despite its achievements, post-operative swelling of the hip and leg is thought to be a contributor to pain and delayed rehabilitation.

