A potential solution to the problems posed by traditional compression stocking is the NCPG. The garment is comprised of a semi-conductive material ground to nanoparticles that are embedded into the fibers, formed into a three-dimensional woven fabric for optimized comfort. Instead of relying on compression, NCPS utilizes the body's own thermal energy to generate infrared energy. The infrared energy generated is reflected back at the body and modifies cellular activity at the level of the mitochondria through a process known as photobiomodulation. This process of photobiomodulation is hypothesized to improve swelling and tissue healing by increasing the activity of mitochondria and the availability of cellular energy in the form of ATP.

WASHINGTON HOSPITAL HEALTHCARE SYSTEM
INSTITUTIONAL REVIEW BOARD

D. Design	
1. (Check all that apply):	
[x] Phase I [] Phase II [] Phase III [] Phase IV [x] Randomized [] Blinded	
[] Behavioral [] Interventional	
[] Multicenter: If so, is Washington Hospital the coordinating center or the primary grant holder?	[] Yes [] No
2. Additional description of general study design . Attach flow diagram if appropriate. Space limit: half page	
Inclusion Criteria	
1. Age range: from 18 to 89	
2. Primary unilateral Total Hip Replacement	
Exclusion Criteria	
1. Physical condition prohibiting use of leg stocking or garment	
2. Allergy to silicone/polyester	
4. Current DVT	
5. History of Vascular Bypass Surgery on Operative Limb ie) Fem-Pop or Fem-Fem	
6. Inability to follow standardized post op and rehab protocols	
7. Lymphedema	
Number of Research Participants	
We will enroll 50 subjects throughout all sites involved in the study.	
E. Data Analysis (How and by whom will data be analyzed?) Space limit: half page	
PI and reparel sponsor will analyze subject questionnaires using statistical data analysis using the results provided by each subject and the PI. Study team will evaluate each criterion and analyze the results of each subject. Routine clinical evaluations will be summarized. The information will be statistically summarized using the criteria identified above and measuring based upon the subject's questionnaires	

WASHINGTON HOSPITAL HEALTHCARE SYSTEM
INSTITUTIONAL REVIEW BOARD

PART 3: PROCEDURES

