	Prisoners
	Inpatients
	Outpatients
	Healthy Volunteers
	Staff of WHHS or WHHS affiliated institutions,
	Students of WHHS
C. Eligibility Criteria:	
1. General description of subject population(s): Elective hip replacement patients.	
2. Inclusion Criteria: 50 subjects age 18-89 years of age. 50% male and 50% female All subjects will have comparable levels of joint arthritis that present imminent surgical options or may present future surgical options. All subjects will be selected by the PI	
3. Exclusion Criteria: Subjects <18 or >90 years of age Subjects determined to be of high risk to participate by PI 1. Physical condition prohibiting use of leg stocking or garment 2. Allergy to silicone/polyester 4. Current DVT 5. History of Vascular Bypass Surgery on Operative Limb ie) Fem-Pop or Fem-Fem 6. Inability to follow standardized post op and rehab protocols 7. Lymphedema	
D. Determination of Eligibility: How (chart review, additional tests/exams for research purposes), when and by whom will eligibility be determined? Subjects will be screened initially by PI/team, for eligibility Consent obtained after participation confirmed. Bioactive sleeve garment and TED stocking supplied at time of surgery Routine clinical followup and questionnaires provided	
E. Are there any inclusion or exclusion criteria based on gender, race or ethnicity ? If “Yes,” please explain the nature and rational for the restrictions below.	
na	

WASHINGTON HOSPITAL HEALTHCARE SYSTEM
INSTITUTIONAL REVIEW BOARD

F. Populations Likely to be Vulnerable to Coercion or Undue Influence: List subject groups who are likely to be vulnerable to coercion or undue influence, such as mentally disabled persons, economically or educationally disadvantaged persons, or investigators' staff or students. For pregnant women, fetuses and neonates, see section 6.G Below: Note: For other vulnerable groups, separate, specific regulations may apply.
na
2. Explain why it is appropriate to include the groups listed above in this particular research:
na

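### Does the BMI limit, stated in the synopsis but not in the visible eligibility lists, leave open who may be enrolled?

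*Protocol*

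**What the plan says.** The Study Population paragraph of the synopsis (Part 2.A) gives an age range and then the sentence "BMI must be below 40".

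Part 2.D lists two inclusion criteria, "Age range: from 18 to 89" and "Primary unilateral Total Hip Replacement". Its exclusion list shows items 1, 2, 4, 5, 6 and 7: a condition that rules out wearing the garment, a material allergy, current DVT, earlier bypass surgery on the operative limb, inability to follow the postoperative protocols, and lymphedema.

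Part 6.C describes the population as elective hip replacement patients. Under inclusion it gives "50 subjects age 18-89 years of age", an even split by sex, a statement on arthritis severity, and selection by the investigator. Under exclusion it adds an age rule and the investigator's judgement of high risk, then repeats the six numbered items with the same gap: "2. Allergy to silicone/polyester 4. Current DVT".

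BMI is named in the synopsis and nowhere else in the text shown.

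**The concern.** A synopsis normally shortens the eligibility section. Here it carries a numeric limit that the two fuller lists do not show. The age limit, which stands in the sentence just before it, does reach both lists, so the omission looks like an oversight. Part 6.C is the form's own eligibility section and the natural place to screen from. A patient with BMI of 40 or more could satisfy everything visible there and still breach the synopsis.

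Two things would be at stake: whether such an enrolment counts as a protocol deviation, and how the study population is described in the report. Bias between arms is not at issue, because the limit makes no reference to allocation and the procedures in Part 3.A identify candidates before randomising them.

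There is also a difference in surgical wording. Part 2.D requires a primary unilateral replacement, whereas Part 6.C.2 says "All subjects will have comparable levels of joint arthritis that present imminent surgical options or may present future surgical options".

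**Working it through.** No arithmetic applies: the protocol gives no BMI data, and no planned figure rests on BMI. The check sets the eligibility statements side by side.

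| Criterion | Synopsis (2.A) | Part 2.D | Part 6.C |
|---|---|---|---|
| BMI | below 40, mandatory | not shown | not shown |
| Age | over 18 and below 90 | 18 to 89 | includes 18 to 89; excludes under 18 or over 90 |
| Surgery | elective hip replacement | primary unilateral hip replacement | elective hip replacement; arthritis wording |
| Six numbered exclusions | not listed | items 1, 2, 4, 5, 6, 7 | items 1, 2, 4, 5, 6, 7 |
| Investigator-judged high risk | not listed | not listed | listed |
| Sex split, arthritis level | not listed | not listed | listed |

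**Is any list complete by itself?** No. Only Part 2.D states primary unilateral surgery. Only Part 6.C gives the high-risk exclusion, the sex split and the arthritis level. Only the synopsis shows the BMI limit. The form divides its criteria among sections, so absence from one section does not cancel a criterion stated in another.

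**Does any section contradict the limit?** No. None allows BMI of 40 or more, gives a different threshold, or says that a list overrides the synopsis. A patient must meet all the stated conditions, and one of them is BMI below 40.

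**What could item 3 be?** Its content is not visible, and the text cannot show whether it was lost in reading the file or removed in the source.

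- If it is a BMI rule, the lists already carry the criterion and, if they use the same threshold, agree with the synopsis.
- If it is something else, or nothing, the synopsis sentence still applies.

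Neither case yields a text that admits a patient with BMI of 40 or more.

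**Is age a clean comparator?** Not quite. Read strictly, the synopsis wants patients older than 18, while the lists admit age 18. Part 6.C includes up to 89 but excludes only above 90, so age 90 falls under neither of its two rules. Age 90 still fails the inclusion range in Parts 2.D and 6.C and the upper limit in the synopsis. Loose repetition between sections is thus general in this form, and nothing singles out BMI as a limit that was dropped on purpose.

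**Does the surgical wording open the study to other patients?** No. Part 2.D states the requirement, Part 6.C.1 limits the population to elective hip replacement, and the arms themselves presuppose one operated leg: "versus bioactive sleeve on nonoperative leg and TED stocking on operative leg".

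**The case for a change.** The best argument for a change is practical. Staff may screen from Part 6.C, and its discretionary items (a condition that rules out the garment, high risk in the investigator's judgement, selection by the investigator) supply no BMI threshold. They make enrolment above the limit less likely but do not state the limit. The same gap at item 3 in two separate lists also fits a deliberate edit in the source at least as well as a reading fault. If a BMI rule was deleted there and the synopsis was left unrevised, the text would no longer reflect the sponsor's intention.

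Part of this stands. The limit is visible only once, and the numbering gap deserves a look at the source file. The rest is conjecture. Nothing in the document shows that item 3 was a BMI rule or that the limit was withdrawn. The idea that someone will screen from one list without the rest of the protocol sits badly with a study whose investigator personally selects every subject. Nor does the argument show that a deviation could not be judged: the mandatory sentence in the synopsis is enough to judge it.

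**Conclusion.** The concern does not hold as a fault in the plan. The observation is accurate for the text shown: the BMI limit appears in the synopsis alone, and item 3 is absent from both exclusion lists. Following the protocol as written nevertheless excludes a patient with BMI of 40 or more, so restating the limit or renumbering the lists would not alter who is eligible. The number of patients who might be screened wrongly cannot be derived, and there is no consequence for the sample size, the endpoints or the comparison of the arms.

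The conclusion assumes that the synopsis is a binding part of the protocol, which its wording supports, and that the lists are not meant to be exhaustive, which nothing contradicts. The age wording and the surgical wording are slips of the same clerical kind, to be reconciled when the form is next edited. This review takes no view on what the BMI limit should be.

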
A. List, in sequence, all research procedures, tests and treatments required for the research. Indicate which would be done even if a subject does not enroll in the research. Include a detailed explanation of any experimental procedures. Attach table if available.
 
1. PI will identify 50 subject candidates willing to participate in the study. 2. Subjects randomized to bioactive sleeve on one leg and TED stocking on other. 3. Routine clinical evaluations performed 4. Patient questionnaires completed 5. Questionnaires and data analyzed, summarized and results presented
	

B. List the specific locations where research procedures will be performed. Indicate how much time will be required of the subjects, per visit and in total for the research.
 
1. PI offices: [name] Orthopedics 2. Normal routine clinical followup, up to 5 minutes for questionnaires
	

C. Will any interviews, questionnaires, surveys or focus groups be conducted for the research? If "Yes," please list any standard instruments used for this research and attach any non-standard instruments. Note: All non-standard instruments must be approved by the WHHS IRB prior to use.
 
Interviews, questionnaires, surveys will be conducted for the research using oral and online communication. Standard instruments: Hoos Jr, Pain Score, Patient Questionnaire, Global 7, Forgotten Joint Score Attached forms: Reparel Patient Questionnaire
	 Yes  No

D. Will subjects or their health care provider be given the results of any experimental tests that are performed for the research? If "Yes" please describe the tests, provide a rationale for providing subjects with the experimental test results and explain what, how and by whom, subjects and their health care provider will be told about the meaning, reliability, and applicability of the test results for health care decisions.
	 Yes  No

WASHINGTON HOSPITAL HEALTHCARE SYSTEM
INSTITUTIONAL REVIEW BOARD

PART 4: ALTERNATIVES

A. Describe the alternatives to research participation that are available to prospective subjects.	
No participation nor research	
B. Is study drug or treatment available off-study? If "Yes", discuss this in the consent form.	 Yes  No  N/A

PART 5: RISKS AND BENEFITS

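### Part 2.B sets an equivalence-or-superiority aim that takes in DVT, but 50 patients randomized to test superiority on pain and scores cannot support either conclusion on DVT

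*Protocol*

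**What the plan says.** - **Part 2.B Purpose** opens: "This prospective study will evaluate pain, swelling, dvt rates as well as narcotic use in post-operative total hip arthroplasty patients". After a sentence on the mixed evidence for compression stockings on pain, swelling and DVT, it sets the aim: "This study will evaluate if NCPS is equivalent, or superior, in these outcome areas". No margin is attached.
- **Part 2.A Synopsis, main hypothesis**, is superiority. The sleeve is expected to "decrease pain and improve patient reported outcome scores faster and more reliably than the control standard TED stocking".
- **Part 2.A, purpose of the sample**: "In order to test this hypothesis, approximately 50 patients scheduled for hip replacement will be randomized to one of two arms". Part 2.D confirms the number: "We will enroll 50 subjects throughout all sites involved in the study".
- **Part 2.A, Primary Objective** compares the two garments "with regard to pain, swelling, and dvt rates". The Primary Endpoint is the set of patient-reported scores, and the next line reads "Secondary Endpoints: Swelling evaluated by routine clinical evaluations. DVT rates monitored".
- **Part 3.A**: "Subjects randomized to bioactive sleeve on one leg and TED stocking on other". Every patient therefore wears both garments, and the randomization decides which one goes on the operative leg.
- **Part 5.E Benefits** lists, among the hoped-for direct benefits, DVT rates that are lower than or comparable with those under the stocking. Again no margin is given.

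**The concern.** The protocol gives two different answers to what the trial may conclude. The Synopsis supports a superiority claim on pain and scores. Part 2.B adds an equivalence claim that reaches DVT, and Part 5.E repeats the idea. DVT also has two ranks: it is part of the primary objective, yet it is a secondary endpoint that is only monitored.

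Under the Part 2.B wording, a null result can be reported as meeting the equivalent half of the aim when the data merely fail to settle the question. DVT is where this matters most. It is a safety outcome, few or no events may occur in 50 patients, and in one arm the sleeve takes the place of the standard stocking on the operative leg. A sentence saying that DVT rates were equivalent would reassure readers without support from the data.

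**Working it through.** **Inputs**
- Total 50 patients, two arms (Parts 2.A and 2.D). The protocol gives no derivation of the 50, so there is no planned figure to reproduce.
- Allocation ratio not stated; 1:1 assumed, so 25 per arm, with no dropout.
- Expected DVT rate not stated. The main check uses the most favourable outcome, no events, and so needs no rate.
- DVT margin not stated; 3 and 5 percentage points are taken as examples of a few points.

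**1. Best case: no events.** With 0 of *n* in each group, the Newcombe (Wilson-based) interval for the difference in proportions has half-width

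z² / (n + z²).

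- Operative legs, n = 25, 95% (z = 1.96, z² = 3.842): 3.842 / 28.842 = 0.133.
- Operative legs, n = 25, 90% (z = 1.645, z² = 2.706): 2.706 / 27.706 = 0.098.
- All legs by garment, n = 50, 95%: 3.842 / 53.842 = 0.071.
- All legs by garment, n = 50, 90%: 2.706 / 52.706 = 0.051.

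**2. One event in each group.** The Newcombe half-width is √[(u − p)² + (p − l)²], where l and u are the Wilson limits.
- 1/25 in each arm, 95%: p = 0.04, l = 0.0071, u = 0.1954, giving 0.159.
- 1/50 in each garment group, 95%: p = 0.02, l = 0.0035, u = 0.1050, giving 0.087.

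| Comparison | Events | 95% CI (points) | 90% CI (points) |
|---|---|---|---|
| Operative legs, 25 v 25 | 0 v 0 | ±13.3 | ±9.8 |
| Operative legs, 25 v 25 | 1 v 1 | ±15.9 | ±12.5 |
| Legs by garment, 50 v 50 | 0 v 0 | ±7.1 | ±5.1 |
| Legs by garment, 50 v 50 | 1 v 1 | ±8.7 | ±6.7 |

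The garment rows ignore the pairing of legs within a patient and mix operative with non-operative legs, so they do not answer the operative-leg question. The 90% column matches an equivalence test at 5% per side, or non-inferiority at one-sided 5%. The 95% column matches non-inferiority at one-sided 2.5%.

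**3. Size needed even with no events.** Setting the half-width equal to a margin m gives n = z²(1 − m)/m.
- m = 5 points: 3.842 × 19 = 73.0, so 73 legs per group at 95%; 2.706 × 19 = 51.4, so 52 at 90%.
- m = 3 points: 3.842 × 32.33 = 124.2, so 125 at 95%; 2.706 × 32.33 = 87.5, so 88 at 90%.

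The trial has 25 operative legs per arm, or 50 legs per garment.

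**4. The superior half of the aim.** Two-sided Fisher exact test, 25 v 25, with all k events in one arm: p = 2 × C(25,k)/C(50,k).
- k = 5: 2 × 53,130 / 2,118,760 = 0.0502.
- k = 6: 2 × 177,100 / 15,890,700 = 0.022.

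Significance at 5% with no event in the sleeve arm therefore needs at least 6 of 25 (24%) in the stocking arm.

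**5. Is no event a realistic outcome?** The chance of no DVT in 50 patients is (1 − rate)⁵⁰. At assumed rates of 1%, 2%, 5% and 10% this is 61%, 36%, 8% and 0.5%. At the lower rates, the outcome most easily misread as equivalence is a common one.

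**The case against.** The strongest reply is that no equivalence test is planned. The form asks for lay language in Part 2, so the phrase may mean no more than at least as good. The main hypothesis is superiority, DVT is secondary and monitored, and Part 2.E says that clinical evaluations will be summarized. The Background restates the purpose as improvement in pain, swelling, range of motion and analgesic use, without DVT or equivalence. A margin could also be set in an SAP that is not shown here.

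Much of this is fair. The missing margin is not the fault by itself, and the lay wording does leave the meaning open. But both readings fail for DVT, because with no events the upper limit of the difference is the same for non-inferiority and for equivalence. An SAP could supply a margin, but it could not make 50 patients enough for one of a few points. The descriptive intent elsewhere in the protocol is a reason to correct Part 2.B, the field where hypotheses and objectives are specified.

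Three stronger readings are tempting, and the document does not support them.
- **That the trial is too small for equivalence on the patient-reported scores.** Part 2.B names pain, swelling, DVT and narcotic use, and not the other scores. Any power figure, for pain included, would rest on a margin that the protocol does not give.
- **That it is too small for swelling.** Each patient wears both garments, and a two-leg comparison within patients could be precise enough.
- **That 73 legs per group is the bar for a 5-point margin.** That figure belongs to a 95% interval. Equivalence at 5% per side needs 52, and the garment comparison with 50 legs comes close at ±5.1 points. It does so only with no events at all and by mixing operative and non-operative legs; one event in each group already gives ±6.7.

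**Conclusion.** The point holds for DVT. Part 2.B states an aim on DVT that differs from the hypothesis the 50 patients are randomized to test and that the design cannot meet. In the best case of no events, operative-leg differences of up to 13.3 points (95%) or 9.8 points (90%) remain open, and superiority would need at least 0 against 6 events. The result rests on 1:1 allocation and no dropout; dropout would only widen the intervals. It does not depend on an assumed DVT rate. It does depend on a relevant margin being a few points: a margin of 10 points would be met on operative legs at 90%, but not at 95%, and only with no events. Part 5.A also notes that every patient wears a TED stocking on one leg and credits this alone with some protection against DVT, which further weakens a reading of similar arm rates as equivalence of the garments.

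The different ranks of DVT and swelling in the primary objective and the endpoint list are a plain inconsistency within Part 2.A. The matter should be fixed, but it affects what may be concluded rather than how the trial is run.

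**What to change.** - **Part 2.B.** Replace the sentence. Suggested text: *The study will evaluate whether NCPS is superior to TED stockings on pain and patient-reported scores. Swelling and narcotic use are secondary outcomes. DVT is monitored and reported descriptively. A non-significant difference is inconclusive and is not evidence of equivalence.* Striking only the word for equivalence would leave a superiority aim on DVT that is equally out of reach.
- **Part 2.A.** Move both DVT and swelling out of the primary objective so that it agrees with the endpoint list, and add narcotic use to the secondary endpoints so that the list agrees with the new Part 2.B.
- **Part 5.E.** Reword the hoped-for DVT benefit so that it does not promise comparability.
- **Reporting.** Give DVT counts by garment and by operative or non-operative leg, with exact 95% confidence intervals and no claim of equivalence.

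The cost is wording only: no added patients, visits or measurements. The sponsor gives up a claim of equivalent or comparable DVT rates. To keep one, it would need a justified margin and a trial sized for it; at 5 points the minimum is 52 (90%) to 73 (95%) operative legs per arm even if no event occurs.

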Traditionally, a standard gradient compression stocking is applied to the leg after surgery to reduce this pain and swelling. However, due to ineffectiveness or patient non-compliance, compression stockings are often not entirely successful at preventing edema. The recently developed NCPS is a lower extremity garment comprised of a technical fabric that is thought to be able to prevent edema and reduce pain all in a comfortable, user-friendly manner. The purpose of this study is to determine if the NCPS is effective at improving post-operative pain, swelling, ROM and analgesic use associated with THA.

Pain and prolonged recovery time associated with post-operative swelling are two factors that contribute to patient dissatisfaction following THA. Swelling of the leg following THA is caused by intraarticular bleeding and inflammation of the periarticular tissues, which can lead to a decrease in functional performance including pain and delayed rehabilitation. Leg swelling can play a part in post-operative quadriceps strength following joint replacement. Ultimately, if post-operative swelling can effectively be reduced, patient recovery could be expedited and patient satisfaction could be improved. Compression stockings have been utilized to attempt to reduce post-operative swelling. Compression works to prevent swelling by reducing the hydrostatic pressure in the leg. Reducing hydrostatic pressure prevents the capillaries from oozing and allows blood to move freely from the superficial to the deep venous system, subsequently allowing excess fluid to flow away from the interstitial space.

More recently, the use of gradient compression stocking following THA has come into question for its efficacy. While the application of external pressure from these gradient compression stocking is beneficial for a period, they are often unable to exert a sufficient amount of pressure long enough to prevent painful edema for an extended amount of time. These garments can show sufficient compression during the first few hours after surgery, but the pressure they applied dropped with time and required daily measurements and refitting to maintain appropriate and therapeutic compression. It's clear that compression stockings are not as effective as once thought when it comes to controlling pain and swelling post-operatively.

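### Part 2.B widens a superiority question to 'equivalent, or superior' against a comparator whose effect the protocol doubts; equivalence to TED cannot show that the sleeve works on pain and swelling

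*Protocol*

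**What the plan says.** **The question.** The main hypothesis in the Synopsis (Part 2.A) is that the sleeve gives less pain and quicker, more reliable gains in patient-reported scores than TED. Randomisation is said to serve that test. Part 2.B, the section reserved for hypotheses and objectives, is wider: "This study will evaluate if NCPS is equivalent, or superior, in these outcome areas". That sentence continues by saying the sleeve may offer a comfortable means of reducing pain and swelling. Part 2.C puts it differently again: "The purpose of this study is to determine if the NCPS is effective at improving post-operative pain, swelling, ROM and analgesic use".

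**The comparator.** Part 2.B treats TED as the current standard of care but adds: "Current literature remains mixed regarding the effectiveness of these stockings in pain, swelling, and dvt reduction". Part 2.C grants that compression helps for a time, then concludes that "compression stockings are not as effective as once thought when it comes to controlling pain and swelling post-operatively". It also reports that "the pressure they applied dropped with time and required daily measurements and refitting to maintain appropriate and therapeutic compression". The description of the intervention in the Synopsis calls the comparator a placebo sleeve.

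**Delivery and reference.** Part 6.D states: "Bioactive sleeve garment and TED stocking supplied at time of surgery". The garment step in Part 3.A reads: "Subjects randomized to bioactive sleeve on one leg and TED stocking on other". In both arms the operated leg wears either the sleeve or TED.

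**The concern.** The trial can estimate one contrast for the operated leg: sleeve effect minus TED effect. A difference near zero is what two working garments would produce, and equally what two inert ones would produce. To read equivalence as efficacy, one must know from elsewhere that TED works for pain and swelling under the conditions of this trial. The protocol supplies no such figure and argues the other way.

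At stake is the conclusion drawn if the arms look alike. As worded, Part 2.B would let that result stand as a positive answer and sit beside a statement about reducing pain and swelling. A missing margin is a separate matter. Any margin limits how far the sleeve may differ from TED; none establishes that TED differs from nothing.

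**Working it through.** The protocol gives no power calculation, SD, margin or expected effect, so there is no planned figure to reproduce. The check is one of logic, followed by an illustration.

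**1. Logic.** Let S be the effect of the sleeve and T the effect of TED, each against no garment on the operated leg.

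- The design estimates S − T. No operated leg is without a garment, so neither S nor T is estimated alone.
- Superiority: if S − T > 0 and TED does no harm (T ≥ 0), then S > 0. A better result than TED therefore supports effectiveness even if TED is weak.
- Equivalence: if S − T is within ±m, then S lies between T − m and T + m. This excludes S = 0 only if T is known to exceed m.
- What the protocol says about T: the literature is mixed (Part 2.B), the effect is smaller than once believed (Part 2.C), and the comparator is in one place a placebo (Part 2.A), which would mean T = 0. No estimate of T is given.

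The condition that equivalence needs is therefore not met on the protocol's own account.

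**2. Illustration: how often two inert garments would look equivalent.** Inputs: 50 patients in total (Part 2.D). Assumed: 1:1 allocation (25 per arm; the ratio is not stated), a 0–10 pain scale, SD 2.0 to 2.5 points, true difference 0.

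- If equivalent is taken to mean no significant difference at two-sided 5%: 1 − 0.05 = 95% of trials, by construction.
- Half-width of the 95% confidence interval = t(0.975, 48) × SD × √(2/25) = 2.011 × 0.283 × SD = 0.569 × SD. This is 1.14 points at SD 2.0 and 1.42 points at SD 2.5.
- Two one-sided tests at 5% each, margin m. In the normal approximation the pass probability is 2Φ(m/se − 1.645) − 1, or zero if negative, with se = SD × √(2/25), i.e. 0.566 or 0.707. For example, m = 2 and SD 2.0: 2/0.566 = 3.536; 3.536 − 1.645 = 1.891; 2 × 0.971 − 1 = 0.94. With the t distribution on 48 degrees of freedom:

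| Margin (points) | SD 2.0 | SD 2.5 |
|---|---|---|
| 1.0 | 10% | 0.4% |
| 1.5 | 67% | 34% |
| 2.0 | 93% | 75% |

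A tight margin makes a pass rarer but does not change its meaning. These rates hold for any trial of this size with no true difference. They are not evidence that TED is inert; they show only that an uninformative equivalence result could easily occur.

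**3. Delivery of TED.** Part 2.C says the stocking "required daily measurements and refitting to maintain appropriate and therapeutic compression". Part 6.D places supply at surgery. Part 3.A has no refitting step. Part 5.B lists telephone calls within 1, 2 and 4 weeks and clinic evaluations at 2, 6 and 12 weeks, without mentioning fit. On the other side, Part 5.C provides standard postoperative care to study patients and Part 6.B ticks inpatients. Refitting is thus neither described nor excluded.

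**The case against.** The strongest reply is that the main hypothesis is already superiority, and that the primary objective is comparative, so the principal test is sound. That is correct: a result better than TED would be evidence of effect. But Part 2.B widens the question, so the protocol gives two answers on which result counts.

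Second, equivalence to standard care has a legitimate use. Part 2.B says TED is hard to put on and that compliance suffers. Whether an easier garment does no worse than usual practice can be asked without proving that TED works. This stands, and the fix leaves room for it. It does not rescue the efficacy reading.

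Third, no single sentence says that equivalence proves effectiveness. True: the link comes from reading Part 2.B with the purpose in Part 2.C. Part 2.B does, however, place the equivalent result and the reduction of pain and swelling in one sentence.

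Fourth, how a null result is worded is often left to the analysis plan or report. Here the protocol itself states what it will evaluate, so the wording is open to correction now.

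A reader might also infer more than the text supports:

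- That the protocol holds TED to be useless. It says less effective than once thought, and helpful for a period; reduced effect is not zero effect.
- That stockings are supplied once, never refitted, and the leg not seen until 2 weeks. Supply at surgery is stated; the rest is not, and inpatient or routine-care refitting may occur.
- That the trial as a whole cannot show efficacy. Only the equivalence route fails.

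**Conclusion.** The point holds for the equivalence reading of pain and swelling, and only for that. The protocol's hypothesis and purpose statements disagree on which result answers the question, and the wider version admits a result that cannot show that either garment works, at any margin. This rests on the protocol's own statements about TED and on every operated leg wearing a garment; it does not rest on the simulated setting. The pass rates (about 93% to 75% with a 2-point margin, 67% to 34% with 1.5 points, 10% to under 1% with 1 point) depend wholly on the assumed 25 per arm, SD and margins, and are illustrative. The test of superiority over TED is unaffected. The placebo and standard-of-care labels conflict with each other, and the refitting statement is not matched by any described procedure; these passages need to be reconciled.

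**What to change.** - In Part 2.B and in the purpose sentence of Part 2.C, follow the Synopsis: for pain and swelling, only superiority over TED will be read as evidence that the sleeve is effective.
- State in advance how a similar result will be reported, for example: no difference from TED shown; the effect of either garment is not established. Similarity to standard care may still be reported alongside comfort or compliance.
- Use one description of the comparator throughout, reconciling the placebo and standard-of-care labels.
- Reconcile the Part 2.C statement on daily measurement and refitting with the supply described in Part 6.D and the procedures in Part 3.A, so that the objective and conclusion name the comparator as actually delivered. Which practice applies is for the investigators to state.

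The cost is a change of wording, with no added patients, arms or procedures. The downside is a less favourable conclusion if the arms do not differ.
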